7. DISCONTINUATION OF STUDY INTERVENTION AND PARTICIPANT DISCONTINUATION/WITHDRAWAL

7.1. Discontinuation of Study Intervention

It may be necessary for a participant to permanently discontinue study intervention. Reasons for permanent discontinuation of study intervention include the following:

- AE requiring discontinuation in investigator's view;
- Pregnancy.

If study intervention is permanently discontinued, the participant will not remain in the study for further evaluation. See the [SoA](#) for data to be collected at the time of discontinuation of study intervention.

In the event of discontinuation of study intervention, it must be documented on the appropriate CRF/in the medical records whether the participant is discontinuing further receipt of study intervention or also from study procedures, further study follow-up, and/or future collection of additional information.

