7.1.1. Potential Cases of Acute Kidney Injury

Participants exposed to IMP demonstrating transient or sustained increase in Screat (with decrease in Screat-based eGFR or eCrCl) require expedited evaluation to differentiate AKI from DICI. DICI is defined as transporter-mediated effect related to altered renal tubular creatinine handling without histological injury.

AKI may be due to one or more types of injury, including DIKI. Differentiation of DIKI from other causes of AKI and from DICI may require clinical, radiographic, histopathologic, and laboratory assessments, as well as nephrology consultation.

Follow-up Assessments

The participant should return to the site for evaluation as soon as possible, preferably within 48 hours of awareness of the abnormal results.

Evaluation should include physical examination, laboratory tests, detailed medical and surgical history, review of all medications (including recreational drugs and supplements [herbal]), family history, sexual history, travel history, blood transfusion, and potential occupational exposure to chemicals.

Laboratory assessments should include simultaneous serum cystatin C (Scys) and serum creatinine (Screat) tests. Estimates of eGFR, eCrCl and Screat-based eGFR and combined Screat-Scys-based eGFR should also be derived using the appropriate equation described in [Appendix 7](#).

Assessments of urine albumin-to-creatinine ratio or urine volume may also be performed as appropriate.

If appropriate, nephrology consultation may be recommended to facilitate differentiation of renal parenchymal disease, pre-renal azotemia, and post-renal obstruction.

If appropriate, nephrology consultation may be recommended to facilitate differentiation of renal parenchymal disease, pre-renal azotemia, and post-renal obstruction.

Differentiating Acute Kidney Injury from DICI

A confirmed Screat increase is defined as:

- (i) $\geq 0.3 \text{ mg/dL}$ ($\geq 26.5 \text{ } \mu\text{mol/L}$) within 48 hours OR
- (ii) confirmed Screat increase ≥ 1.5 times baseline (known or suspected to have occurred within the prior 7 days).

Based on the assessments performed, suspected AKI (including DIKI) may be differentiated from DICI as follows.

Adult participants

	AKI (including DIKI) Any one of the below	DICI

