7.1.2. Liver Injury

A participant who meets the criteria of potential DILI (Hy's law) case as described in [Appendix 5](#) in Section [10.5](#) will be withdrawn from the study intervention.

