7.2. Participant Discontinuation/Withdrawal From the Study

A participant may withdraw from the study at any time at their own request. Reasons for discontinuation from the study include the following:

- Refused further study procedures;
- Lost to follow-up;
- Death;

- Study terminated by sponsor;
- Pregnancy;
- Behavioral, compliance, or administrative reasons.

At the time of discontinuing from the study, if possible, an early discontinuation visit should be conducted. See the [SoA](#) for assessments to be collected at the time of study discontinuation and follow-up and for any further evaluations that need to be completed.

The early discontinuation visit applies only to participants who are enrolled/randomized and then are prematurely withdrawn from the study. Participants should be questioned regarding their reason for withdrawal.

The participant will be permanently discontinued from the study intervention and the study at that time.

If a participant withdraws from the study, they may request destruction of any remaining samples taken and not tested, and the investigator must document any such requests in the site study records and notify the sponsor accordingly.

If the participant withdraws from the study and also withdraws consent (see Section 7.2.1 for disclosure of future information, no further evaluations will be performed and no additional data will be collected. The sponsor may retain and continue to use any data collected before such withdrawal of consent.

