8.4.1. Time Period and Frequency for Collecting AE and SAE Information

The time period for actively eliciting and collecting AEs and SAEs (“active collection period”) for each participant begins from the time the participant provides informed consent, which is obtained before undergoing any study-related procedure and/or receiving study intervention), through and including a minimum of 28 calendar days, except as indicated below, after the last administration of the study intervention.

Follow-up by the investigator continues throughout the active collection period and until the AE or SAE or its sequelae resolve or stabilize at a level acceptable to the investigator.

When a clinically important AE remains ongoing at the end of the active collection period, follow-up by the investigator continues until the AE or SAE or its sequelae resolve or stabilize at a level acceptable to the investigator and Pfizer concurs with that assessment.

For participants who are screen failures, the active collection period ends when screen failure status is determined.

If the participant withdraws from the study and also withdraws consent for the collection of future information, the active collection period ends when consent is withdrawn.

If a participant permanently discontinues or temporarily discontinues study intervention because of an AE or SAE, the AE or SAE must be recorded on the CRF and the SAE reported using the CT SAE Report Form.

Investigators are not obligated to actively seek information on AEs or SAEs after the participant has concluded study participation. However, if the investigator learns of any SAE, including a death, at any time after a participant has conducted the study participation, and they consider the event to be reasonably related to the study intervention, the investigator must promptly report the SAE to Pfizer using the CT SAE Report Form.

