- For participants with baseline AST **OR** ALT **OR** T bili values above the ULN, the following threshold values are used in the definition mentioned above, as needed, depending on which values are above the ULN at baseline:
 - Preexisting AST or ALT baseline values above the normal range: AST or ALT values ≥ 2 times the baseline values AND $\geq 3 \times$ ULN; or $\geq 8 \times$ ULN (whichever is smaller).

- Preexisting values of T bili above the normal range: T bili level increased from baseline value by an amount of $\geq 1 \times$ ULN **or** if the value reaches $\geq 3 \times$ ULN (whichever is smaller).

Rises in AST/ALT and T bili separated by more than a few weeks should be assessed individually based on clinical judgment; any case where uncertainty remains as to whether it represents a potential Hy's law case should be reviewed with the sponsor.

The participant should return to the investigator site and be evaluated as soon as possible, preferably within 48 hours from awareness of the abnormal results. This evaluation should include laboratory tests, detailed history, and physical assessment.

In addition to repeating measurements of AST and ALT and T bili for suspected Hy's law cases, additional laboratory tests should include albumin, CK, direct and indirect bilirubin, GGT, PT/INR, eosinophils (%), and alkaline phosphatase. Consideration should also be given to drawing a separate tube of clotted blood and an anticoagulated tube of blood for further testing, as needed, for further contemporaneous analyses at the time of the recognized initial abnormalities to determine etiology. A detailed history, including relevant information, such as review of ethanol, acetaminophen/paracetamol (either by itself or as a coformulated product in prescription or over-the-counter medications), recreational drug, or supplement (herbal) use and consumption, family history, sexual history, travel history, history of contact with a jaundiced person, surgery, blood transfusion, history of liver or allergic disease, and potential occupational exposure to chemicals, should be collected. Further testing for acute hepatitis A, B, C, D, and E infection, total bile acids, liver imaging (eg, biliary tract), and collection of serum samples for acetaminophen/paracetamol drug and/or protein adduct levels may be warranted.

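### Section 7.1 ends study participation for anyone who permanently stops drug, which contradicts the safety follow-up required elsewhere for participants stopped for an adverse event

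*Protocol*

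**What the plan says.** Protocol section 7.1 lists two reasons for permanently stopping drug: an AE that in the investigator's view requires it, and pregnancy. It then says: "If study intervention is permanently discontinued, the participant will not remain in the study for further evaluation". The next sentence points to the Schedule of Activities for data to collect at discontinuation. The paragraph after that asks the site to document "whether the participant is discontinuing further receipt of study intervention or also from study procedures, further study follow-up", among other things.

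Other sections set duties that run past the last dose:

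- **Section 8.4.1** collects AEs and serious AEs from consent "through and including a minimum of 28 calendar days, except as indicated below, after the last administration of the study intervention". It adds that if a participant "withdraws from the study and also withdraws consent for the collection of future information, the active collection period ends when consent is withdrawn".
- **Section 8.4.3** requires each event to be pursued until it resolves, stabilizes or is otherwise explained, or the participant is lost to follow-up.
- **Schedule of Activities (Table 1 notes) and section 4.1** set a contact 28 to 35 days after the last dose. The Table 1 note makes it mandatory and allows it by telephone.
- **Section 7.1.2** covers "A participant who meets the criteria of potential DILI" under Hy's law and takes that person off drug. **Appendix 5** says: "The participant should return to the investigator site and be evaluated as soon as possible".
- **Section 7.1.1**, for a creatinine rise, says: "The participant should return to the site for evaluation as soon as possible, preferably within 48 hours of awareness of the abnormal results".
- **Section 7.2**, for participants leaving the study, refers to the Schedule of Activities "for assessments to be collected at the time of study discontinuation and follow-up and for any further evaluations that need to be completed".
- **Section 7.2.1** keeps participants who ask to stop drug in the study and requires that they still be followed, unless they withdraw consent to further contact.

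**The concern.** A site consults section 7.1 at the moment drug is stopped. For a participant stopped because of harm, its plain instruction is that evaluation ends, while several other sections require it to continue. A participant who simply chooses to stop is followed under 7.2.1; one stopped for an AE, on the words of 7.1, is not.

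Safety and tolerability are a secondary objective, and SAP section 3.5.1 counts events as treatment-emergent up to 28-35 days after the last dose. If a site follows 7.1 literally, that window is unobserved after the early-termination visit for exactly the participants who are most informative about tolerability. Two things could be lost: AEs that start after that visit, and the outcome of the AE that caused the stop. The stopping AE itself would still be on the case report form, because 8.4.1 requires it to be recorded.

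The liver case is the sharpest. Section 2.2.3 names the hepatobiliary system as the key target organ in adult animals, and a potential Hy's law case needs repeat tests after drug is stopped.

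**Working it through.** The plan gives no figure to reproduce on this point. The check sets the 7.1 rule beside each other rule and asks whether a site can obey both for a participant permanently stopped for an AE.

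| Other rule | What it requires after the last dose | Exemption for early stoppers? | Compatible with 7.1 as written? |
|---|---|---|---|
| 8.4.1, collection period | At least 28 days of AE collection | None; the early ends listed are screen failure and withdrawal of consent | No |
| 8.4.3 | Each event followed to an outcome | None; leaving the study is not a listed end point | No |
| Schedule of Activities, 4.1 | Contact at 28 to 35 days | None | No |
| 7.1.2 with Appendix 5 | Off drug, then return for evaluation, preferably within 48 hours | None | No |
| 7.1.1 | Return for evaluation, preferably within 48 hours | None | No, if drug was stopped for the kidney finding; 7.1.1 does not itself order a stop |
| 7.1, documentation paragraph | Record whether only drug, or also follow-up, is stopped | Not applicable | No; the choice is empty if everyone exits |
| 7.2.1 | Participants who ask to stop drug stay in and are followed | Only if consent to contact is withdrawn | Opposite rule |

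**Can the early-termination visit fill the gap?** The Schedule of Activities gives it safety laboratory tests, an ECG, vital signs, a PK sample and a contraception check. That is a single visit. If the last dose is on Day d, the contact is due from Day d + 28 to Day d + 35. As an illustration, a last dose on Day 5 puts it on Day 33 to Day 40. A visit at the time of discontinuation cannot observe that period.

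**Can confinement fill it?** Dosing runs from Day 1 to Day 8 and discharge is on Day 11. Even a participant who stayed until discharge would be observed for 11 − 8 = 3 days to 11 − 1 = 10 days after the last dose, against the required 28.

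**Does 8.4.1 reconcile the texts?** It says investigators need not actively seek AEs once a participant has concluded participation. If a 7.1 exit counts as conclusion, that sentence cancels the 28-day minimum for participants stopped for an AE. The section does not list this as an exception, and 8.4.3 would still conflict.

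**Size.** One affected participant among about 12 in the safety set is 1/12 = 8.3%. No expected rate of discontinuation for AEs is given, so no study-level figure can be derived.

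**The case against.** The strongest answer is that leaving the study and being followed for safety are compatible. Section 8.4.1 ends collection at study exit only when consent is also withdrawn, and 7.2 sends participants who exit to the Schedule of Activities for follow-up. On that view 7.1 ends only dosing and PK profiles. The sentence after the disputed one also points to the Schedule of Activities, where AE monitoring runs through the final columns and the late contact is mandatory, so a site reading all of 7.1 would find the right instruction.

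The exposure is narrow too. The rule can bite only while doses remain, between Day 1 and Day 8. Potential Hy's law cases are reported as serious AEs and so are followed under 8.4.3, and section 8.3.5 has clinically significant abnormal results repeated until they settle. Appendix 5 notes that transaminase rises usually precede bilirubin rises by days or weeks, so a case may first appear when no dose is left to stop. Section 2.2.4 reports no serious AEs attributed to the drug; the most common related events were gastrointestinal, mild to moderate, and resolved. Section 2.3.1 describes liver enzyme rises as mild and transient, in a few participants.

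Much of this stands. The follow-up duties do survive, the practical risk is small, the conflict with 7.1.1 is conditional, and the documentation paragraph prompts the site to address follow-up. What does not stand is the reading that 7.1 ends only dosing and PK sampling: the sentence says the participant leaves the study and is not evaluated further. The pointer to the Schedule of Activities concerns data at the time of discontinuation. Needing four other sections to override the one on stopping drug is the defect.

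**Conclusion.** The concern holds. Section 7.1 states a rule that contradicts sections 8.4.1 and 8.4.3, the 28-35 day contact, and section 7.1.2 read with Appendix 5. It also contradicts 7.1.1 where drug is stopped for a kidney finding, and it runs opposite to 7.2.1.

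The consequence depends on a site applying 7.1 literally. For each such participant, the required 28 days of AE collection and the late contact would be lost after the early-termination visit. The 8.3% figure describes one participant in a safety set of about 12; it is not an estimate of how often this will happen. The primary PK endpoints and the sample size are not affected. The wording should be corrected because it concerns safety follow-up of participants stopped for harm and the correction costs almost nothing.

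**What to change.** Edit section 7.1 only. Replace the sentence with:

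> If study intervention is permanently discontinued, no further doses are given and scheduled PK sampling ends with the early-termination visit. Early-termination assessments, the evaluations in 7.1.1 and Appendix 5 where they apply, AE collection and follow-up under 8.4.1 and 8.4.3, and the 28-35 day contact continue unless the participant withdraws consent for follow-up, dies or is lost to follow-up; pregnancies are followed under 8.4.5.1.

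Section 8.4.1 needs no change: a participant who stays in safety follow-up has not concluded participation, so its release from actively seeking AEs does not apply. The SAP needs no change either.

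The cost is a rewording at one place in one section. Every item in the new text is already required elsewhere in the protocol, and the late contact may be by telephone.

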7.1.1. Potential Cases of Acute Kidney Injury

Participants exposed to IMP demonstrating transient or sustained increase in Screat (with decrease in Screat-based eGFR or eCrCl) require expedited evaluation to differentiate AKI from DICI. DICI is defined as transporter-mediated effect related to altered renal tubular creatinine handling without histological injury.

AKI may be due to one or more types of injury, including DIKI. Differentiation of DIKI from other causes of AKI and from DICI may require clinical, radiographic, histopathologic, and laboratory assessments, as well as nephrology consultation.

Follow-up Assessments

The participant should return to the site for evaluation as soon as possible, preferably within 48 hours of awareness of the abnormal results.

Evaluation should include physical examination, laboratory tests, detailed medical and surgical history, review of all medications (including recreational drugs and supplements [herbal]), family history, sexual history, travel history, blood transfusion, and potential occupational exposure to chemicals.

Laboratory assessments should include simultaneous serum cystatin C (Scys) and serum creatinine (Screat) tests. Estimates of eGFR, eCrCl and Screat-based eGFR and combined Screat-Scys-based eGFR should also be derived using the appropriate equation described in [Appendix 7](#).

Assessments of urine albumin-to-creatinine ratio or urine volume may also be performed as appropriate.

If appropriate, nephrology consultation may be recommended to facilitate differentiation of renal parenchymal disease, pre-renal azotemia, and post-renal obstruction.

If appropriate, nephrology consultation may be recommended to facilitate differentiation of renal parenchymal disease, pre-renal azotemia, and post-renal obstruction.

Differentiating Acute Kidney Injury from DICI

A confirmed Screat increase is defined as:

- (i) $\geq 0.3 \text{ mg/dL}$ ($\geq 26.5 \text{ } \mu\text{mol/L}$) within 48 hours OR
- (ii) confirmed Screat increase ≥ 1.5 times baseline (known or suspected to have occurred within the prior 7 days).

Based on the assessments performed, suspected AKI (including DIKI) may be differentiated from DICI as follows.

Adult participants

	AKI (including DIKI) Any one of the below	DICI
Scys & Screat	Simultaneous, confirmed serum cystatin C (Scys) increase and confirmed Screat increase	Confirmed Screat increase without confirmed increase in reflex Scys AND Confirmed Screat-based eGFR decrease without confirmed combined Screat-Scys-based eGFR decrease.
eGFR	Decrease in Screat-based eGFR and combined Screat-Scys-based eGFR (when available)	
Albuminuria or proteinuria	Confirmed albuminuria increase (see Appendix 6 for Grades A1 to A3 quantitation)	
Urine volume	Urine volume $<0.5 \text{ mL/kg/h}$ for 6 consecutive hours	

Regardless of the presence or absence of increase in Scrat, DIKI and other causes of AKI may be suspected if either there is (i) new-onset or worsening albuminuria or proteinuria are detected or (ii) urine volume (if measured) is <0.5 mL/kg/h for 6 consecutive hours.

All confirmed cases of clinically relevant decrease in kidney function should be considered potential cases of DIKI if no other reason for the kidney function abnormalities has been found.

7.1.2. Liver Injury

A participant who meets the criteria of potential DILI (Hy's law) case as described in [Appendix 5](#) in Section [10.5](#) will be withdrawn from the study intervention.

7.1.3. ECG Changes

A participant who meets either bulleted criterion based on the average of ECG readings will be withdrawn from the study intervention.

- QTcF >500 ms.
- Change from baseline: QTcF >60 ms.

If a clinically significant finding is identified (including, but not limited to, changes from baseline in QTcF after enrollment), the investigator or qualified designee will determine if the participant can continue in the study and if any change in participant management is needed. This review of the ECG printed at the time of collection must be documented. Any new clinically relevant finding should be reported as an AE.

7.1.4. COVID-19

If a participant has COVID-19 during the study, this should be reported as an AE or SAE (as appropriate) and appropriate medical intervention provided. Temporary discontinuation of the study intervention may be medically appropriate until the participant has recovered from COVID-19.

It is recommended that the investigator discuss temporary or permanent discontinuation of study intervention with the study medical monitor.

7.2. Participant Discontinuation/Withdrawal From the Study

A participant may withdraw from the study at any time at their own request. Reasons for discontinuation from the study include the following:

- Refused further study procedures;
- Lost to follow-up;
- Death;

- Study terminated by sponsor;
- Pregnancy;
- Behavioral, compliance, or administrative reasons.

At the time of discontinuing from the study, if possible, an early discontinuation visit should be conducted. See the [SoA](#) for assessments to be collected at the time of study discontinuation and follow-up and for any further evaluations that need to be completed.

The early discontinuation visit applies only to participants who are enrolled/randomized and then are prematurely withdrawn from the study. Participants should be questioned regarding their reason for withdrawal.

The participant will be permanently discontinued from the study intervention and the study at that time.

If a participant withdraws from the study, they may request destruction of any remaining samples taken and not tested, and the investigator must document any such requests in the site study records and notify the sponsor accordingly.

If the participant withdraws from the study and also withdraws consent (see Section 7.2.1 for disclosure of future information, no further evaluations will be performed and no additional data will be collected. The sponsor may retain and continue to use any data collected before such withdrawal of consent.

